### 6.6.2. Laboratory Data

Laboratory test values for individual subjects will be listed. The observed laboratory values and change from baseline over time, shifts in clinical laboratory tests and subjects with laboratory test abnormalities will be summarized by treatment group.

### 6.6.3. Vital Signs

Descriptive statistics will be used to summarize seated blood pressure (systolic and diastolic) and seated pulse rate (bpm).

### 6.6.4. Electrocardiograms

*Changes from baseline for the ECG parameters QT interval, heart rate, QTc interval, PR interval, and QRS complex will be summarized by treatment and visit.*

*The number (%) of participants with maximum QTc values and maximum increases from baseline in the following categories will be tabulated by treatment:*

#### Safety QTc Assessment

Degree of Prolongation	Mild (msec)	Moderate (msec)	Severe (msec)
Absolute value	>450-480	>480-500	>500
Increase from baseline		30-60	>60

*In addition, the number of participants with uncorrected QT values >500 msec will be summarized.*

### 6.6.5. Body Weight

Baseline body weight and change from baseline in body weight at Week 24 will be summarized.

## 7. INTERIM ANALYSES

### 7.1. Introduction

*An interim analysis will be performed to assess efficacy and safety. The interim analysis will take place approximately 16 weeks after 50% of the planned participants (ie, approximately 110 participants), with the exception of the 160 mg Q2W group, are randomized. Interim analysis results, which will include all available data from enrolled participants at the time of data cutoff, may be used for internal business decisions regarding future study planning or adapting the study after the interim analysis. Before any interim analysis is instigated, the details of the objectives, decision criteria, dissemination plan, and method of maintaining the study blind as per Pfizer's SOPs will be documented and approved in a DMC charter.*

## 7.2. Interim Analyses and Summaries

In addition to DMC safety tables, the demographic and baseline characteristics tables described in 6.5.1. will be provided.

The following endpoints will be summarized by treatment group at the interim analyses:

- Percent change from baseline in non-HDL-C at Week 16;
- Percent change from baseline in TG at Week 16;
- Percent change from baseline in ApoB at Week 16;
- Percent change from baseline in LDL-C at Week 16;
- Percent change from baseline in ANGPTL3 at Week 16.

Since no decision rules of futility or early stopping for success is planned for the IA, no hypothesis testing will be conducted. Bayesian probabilities of having at least one vupanorsen group achieve the following targets will be calculated respectively.

- $\geq 35\%$  reduction in non-HDL-C;
- $\geq 75\%$  reduction in ANGPTL3.

## 9. APPENDICES

### Appendix 1. Summary of Efficacy Analyses

Endpoint	Analysis Type	Estimand	Population	Data Inclusion and Rules for Handling Intercurrent Events and Missing Data	Analysis Model	Explicit Imputation
Percent change from baseline in non-HDL-C at Week 24	Main analysis	Hypothetical	FAS_primary	Data collected post occurrence of intercurrent events will be excluded from analysis.	MMRM	N
Percent change from baseline in non-HDL-C at Week 24	Supplementary analysis	Principal Stratum	FAS_ps	All data collected in the placebo group will be included regardless of intercurrent events; Subjects who experience intercurrent events in the vupanorsen groups will be excluded from analysis.	The principal stratum estimand approach	N
Percent change from baseline in non-HDL-C at Week 24	Supplementary analysis	TP	FAS	All data collected will be included regardless of intercurrent events	MMRM	N
Percent change from baseline in non-HDL-C at Week 24	Supplementary analysis	TP	FAS	All data collected will be included regardless of intercurrent events	MI-RD	Y
Percent change from baseline in non-HDL-C at Week 24	Sensitivity analysis	Hypothetical	FAS_primary	Data collected post occurrence of intercurrent events will be excluded from analysis.	RTB	Y
Percent change from baseline in non-HDL-C at Week 24	Dose-response analysis	NA	FAS_primary	Data collected post occurrence of intercurrent events will be excluded from analysis.	Bayesian Emax	N
Percent change from baseline in TG at Week 24	Main analysis	Hypothetical	FAS_primary	Data collected post occurrence of intercurrent events will be excluded from analysis.	MMRM	N
Percent change from baseline in TG at Week 24	Supplementary analysis	Principal Stratum	FAS_ps	All data collected in the placebo group will be included regardless of intercurrent events; Subjects who experience intercurrent events	The principal stratum estimand approach	N

Endpoint	Analysis Type	Estimand	Population	Data Inclusion and Rules for Handling Intercurrent Events and Missing Data	Analysis Model	Explicit Imputation
				in the vupanorsen groups will be excluded from analysis.		
Percent change from baseline in TG at Week 24	Supplementary analysis	TP	FAS	All data collected will be included regardless of intercurrent events	MMRM	N
Percent change from baseline in TG at Week 24	Supplementary analysis	TP	FAS	All data collected will be included regardless of intercurrent events	MI-RD	Y
Percent change from baseline in TG at Week 24	Sensitivity analysis	Hypothetical	FAS_primary	Data collected post occurrence of intercurrent events will be excluded from analysis.	RTB	Y
Percent change from baseline in TG at Week 24	Dose-response analysis	NA	FAS_primary	Data collected post occurrence of intercurrent events will be excluded from analysis.	Bayesian Emax	N
Percent change from baseline in ApoB at Week 24	Main analysis	Hypothetical	FAS_primary	Data collected post occurrence of intercurrent events will be excluded from analysis.	MMRM	N
Percent change from baseline in ApoB at Week 24	Supplementary analysis	Principal Stratum	FAS_ps	All data collected in the placebo group will be included regardless of intercurrent events; Subjects who experience intercurrent events in the vupanorsen groups will be excluded from analysis.	The principal stratum estimand approach	N
Percent change from baseline in ApoB at Week 24	Supplementary analysis	TP	FAS	All data collected will be included regardless of intercurrent events	MMRM	N
Percent change from baseline in ApoB at Week 24	Supplementary analysis	TP	FAS	All data collected will be included regardless of intercurrent events	MI-RD	Y
Percent change from baseline in ApoB at Week 24	Sensitivity analysis	Hypothetical	FAS_primary	Data collected post occurrence of intercurrent events will be excluded from analysis.	RTB	Y

Endpoint	Analysis Type	Estimand	Population	Data Inclusion and Rules for Handling Intercurrent Events and Missing Data	Analysis Model	Explicit Imputation
Percent change from baseline in LDL-C at Week 24	Main analysis	Hypothetical	FAS_primary	Data collected post occurrence of intercurrent events will be excluded from analysis.	MMRM	N
Percent change from baseline in LDL-C at Week 24	Supplementary analysis	Principal Stratum	FAS_ps	All data collected in the placebo group will be included regardless of intercurrent events; Subjects who experience intercurrent events in the vupanorsen groups will be excluded from analysis.	The principal stratum estimand approach	N
Percent change from baseline in LDL-C at Week 24	Supplementary analysis	TP	FAS	All data collected will be included regardless of intercurrent events	MMRM	N
Percent change from baseline in LDL-C at Week 24	Supplementary analysis	TP	FAS	All data collected will be included regardless of intercurrent events	MI-RD	Y
Percent change from baseline in LDL-C at Week 24	Sensitivity analysis	Hypothetical	FAS_primary	Data collected post occurrence of intercurrent events will be excluded from analysis.	RTB	Y
Percent change from baseline in ANGPTL3 at Week 24	Main analysis	Hypothetical	FAS_primary	Data collected post occurrence of intercurrent events will be excluded from analysis.	MMRM	N
Percent change from baseline in ANGPTL3 at Week 24	Supplementary analysis	Principal Stratum	FAS_ps	All data collected in the placebo group will be included regardless of intercurrent events; Subjects who experience intercurrent events in the vupanorsen groups will be excluded from analysis.	The principal stratum estimand approach	N
Percent change from baseline in ANGPTL3 at Week 24	Supplementary analysis	TP	FAS	All data collected will be included regardless of intercurrent events	MMRM	N

Endpoint	Analysis Type	Estimand	Population	Data Inclusion and Rules for Handling Intercurrent Events and Missing Data	Analysis Model	Explicit Imputation
Percent change from baseline in ANGPTL3 at Week 24	Supplementary analysis	TP	FAS	All data collected will be included regardless of intercurrent events	MI-RD	Y
Percent change from baseline in ANGPTL3 at Week 24	Sensitivity analysis	Hypothetical	FAS_primary	Data collected post occurrence of intercurrent events will be excluded from analysis.	RTB	Y
Percent change from baseline in ANGPTL3 at Week 24	Dose-response analysis	NA	FAS_primary	Data collected post occurrence of intercurrent events will be excluded from analysis.	Bayesian Emax	N

## Appendix 2. Data Derivation Details

### Appendix 2.1. Definition and Use of Visit Windows in Reporting

Visit	Target Day	Visit Window
Baseline	1	Screening to Day 1
Week 4	29	Day 15 to Day 42
Week 8	57	Day 43 to Day 70
Week 12	85	Day 71 to Day 98
Week 16	113	Day 99 to Day 126
Week 20	141	Day 127 to Day 154
Week 24	169	Day 155 to Day 182
12-week follow-up	Week 32 for Q4W: 225	Day 211 to Day 238
	Week 34 for Q2W: 239	Day 225 to Day 252

## Appendix 3. List of Abbreviations

Abbreviation	Term
Abs	absolute
AE	adverse event
ANCOVA	analysis of covariance
ANOVA	analysis of variance
ATC	Anatomic Therapeutic Chemical
AUC	area under the curve
BA	bioavailability
BE	bioequivalence
BLQ	below the limit of quantitation
BOCF	baseline observation carried forward
BP	blood pressure
CDARS	Clinical Data Analysis and Reporting System (of US Food and Drug Administration)
CI	confidence interval
C max	maximum observed concentration
CMH	Cochran-Mantel-Haenszel
CRF	case report form
CSR	clinical study report
DMC	data monitoring committee
EAC	event adjudication committee
ECG	electrocardiogram
E-DMC	external data monitoring committee
FAS	full analysis set
FDA	Food and Drug Administration (United States)
GCP	Good Clinical Practice
GLIMMIX	generalized linear mixed-effects model with repeated measures

Abbreviation	Term
GMC	geometric mean concentration
GMFR	geometric mean fold rise
GMR	geometric mean ratio
GMT	geometric mean titer
ICD	informed consent document
ICH	International Council for Harmonisation
IRC	internal review committee
IST	independent statistical team
ITT	intent-to-treat
LLOQ	lower limit of quantitation
LOCF	last observation carried forward
LOD	limit of detection
LS	least-squares
LSM	least-squares mean
MAR	missing at random
MedDRA	Medical Dictionary for Regulatory Activities
mITT	modified intent-to-treat
MI-RD	Multiple imputation based on retrieved dropouts
MMRM	mixed-effects model with repeated measures
MNAR	missing not at random
N/A	not applicable
NNB	number needed to benefit
NNH	number needed to harm
NNT	number needed to treat
NOAEL	no-observed-adverse-effect level
PD	pharmacodynamic(s)
PK	pharmacokinetic(s)
PP	per-protocol
PPAS	per-protocol analysis set
PRO	patient-reported outcome
PT	preferred term
QTc	corrected QT
QTcF	corrected QT (Fridericia method)
qual	qualitative
RCDC	reverse cumulative distribution curve
RR	relative risk
RTB	Return to baseline
SAE	serious adverse event
SAP	statistical analysis plan
SD	standard deviation
SGS	Statistical Guidance Standards
SOP	standard operating procedure
SUSAR	suspected unexpected serious adverse reaction

Abbreviation	Term
TA	therapeutic area
ULN	upper limit of normal
WHO	World Health Organization
WHODD	World Health Organization Drug Dictionary

#### Appendix 4. Example SAS code

##### MMRM:

```
proc mixed data=adeff method=reml;
class subjid avisitn trt01pn;
model chg=base trt01pn avisitn trt01pn*avisitn/ddfm=kr s;
repeated avisitn/sub=subjid type=un;
run;
```

##### Bayesian dose-response model:

```
proc mcmc data=adeff nbi=10000 nmc=5000000 thin=50 seed=12345
monitor=(e0 ed50 emax sigma dose_80 dose_120 dose_160 dose_240 dose_320
);
/*x1-x4 are starting values for precision and parameters of Emax dose-
response model*/
parms precision x1;
parms e0 x2;
parms ed50 x3;
parms emax x4;
prior precision~normal(xx, xx, lower=0);
prior e0~normal(xx, xx);
prior ed50 ~normal(xx, xx);
prior emax ~normal (xx, xx);
BEGINNODATA ;
dose_80=e0+emax*80/(80+ed50);
dose_120=e0+emax*120/(120+ed50);
dose_160=e0+emax*160/(160+ed50);
dose_240=e0+emax*240/(240+ed50);
dose_320=e0+emax*320/(320+ed50);
sigma=1/sqrt(precision);
ENDNODATA ;

mu=e0+emax*dose/(dose+ed50);
model y~normal(mu, sigma);
run;
```

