## 4.2. Scientific Rationale for Study Design

As reviewed in the IB, vupanorsen demonstrated significant reductions in TG and multiple lipid endpoints in the Phase 2a study in participants with hypertriglyceridemia, NAFLD, and diabetes; however, the maximal reduction in ANGPTL3 achieved with the highest dose of 80 mg Q4W in the study was below the magnitude needed to observe maximal lipid lowering with this mechanism (ie,  $\geq 75\%$  ANGPTL3 reduction). From a safety perspective, the numerical increases in liver fat at 20 mg QW and 40 mg Q4W, along with the larger increase noted at 80 mg Q4W need to be further evaluated.

In the current study, the participant population is focused on those with elevated non-HDL-C and TG and are on a stable dose of a statin to determine the optimum dose for future development for hypertriglyceridemia and CV risk reduction. To further evaluate potential changes in liver fat accumulation, participants will complete MRI-PDFF at Screening and end of treatment (Week 24). In addition, banked biospecimens will be collected and stored for further analyses which may, for example, provide greater understanding of vupanorsen.

Vupanorsen has an unlikely risk of human teratogenicity/fetotoxicity. However, participants who are WOCBP must use an acceptable contraceptive method (see [Appendix 4](#)). The risk of vupanorsen causing damage to the DNA of sperm is considered low, and the risk of exposure to vupanorsen in a sexual partner of a male participant in this study via ejaculate is low; therefore, no contraception (condom) use in male participants is required (see [Appendix 4](#)). The highest dose of vupanorsen planned for this study would result in maternal systemic exposures via seminal transfer well below ( $>5000$ -fold) the exposure at the NOAEL for developmental toxicity in nonclinical studies, including the conservative assumptions that an ASO ejaculate:serum ratio would be 1 and there is 100% uptake by the partner.

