In addition to the primary analysis, the following three supplementary analyses will be conducted for additional evaluation of the primary and key secondary endpoints (ie, evaluated at Week 24). The first two, one using the MMRM model and the other using the multiple imputation using retrieved dropouts (MI-RD) approach, based on the TP estimand will be applied to the FAS (ie, including data collected post occurrence of intercurrent events as defined in [Section 2.1.3.1](#)). The last one, will be conducted in the framework of the principal stratum estimand, with details to be described in [Section 5.2.1.1](#). One sensitivity missing data analysis ([Section 5.3](#)) under the assumption of missing not at random (MNAR) will be implemented to evaluate the robustness of the primary results, for primary and key secondary endpoints. As in the primary analysis, both supplementary and sensitivity analyses will report the estimates for treatment arms.

Apart from the above statistical efficacy analyses, a Bayesian dose-response model will be constructed to model the relationship between percent change from baseline at Week 24 and doses listed in [Table 3](#), along with estimated 95% CI, for each of the primary and selected key secondary endpoints ([Appendix 1](#)) respectively. The parameter estimates from the phase 2a study will inform the model estimation, ie, used as prior distribution of the 3 parameters (E0, Emax, ED50) and the standard deviation of the residual term.

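### The SAP's only Emax specification leaves ED50 free to go negative and plans no check on its Phase 2a prior: a small specification gap in a supplementary model

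*SAP*

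**What the plan says.** SAP Section 5.2.1 plans a Bayesian dose-response model for percent change at Week 24 against total monthly dose. Appendix 1 lists it for non-HDL-C, TG and ANGPTL3. On the prior, Section 5.2.1 says: "The parameter estimates from the phase 2a study will inform the model estimation, ie, used as prior distribution of the 3 parameters". Protocol 9.4.2 names the same source. Neither text gives prior variances, a discount, a positivity constraint or an alternative prior. Appendix 1 lists sensitivity and supplementary analyses of the Week 24 endpoints but none for the Emax fits.

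SAP Appendix 4, labelled "Example SAS code", supplies the model "mu=e0+emax*dose/(dose+ed50" with these priors:

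- precision: "prior precision~normal(xx, xx, lower=0", so bounded at zero;
- ED50: "prior ed50 ~normal(xx, xx", with no bound;
- Emax: "prior emax ~normal (xx, xx", entered separately from ED50.

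On Phase 2a, Protocol 4.2 says "the maximal reduction in ANGPTL3 achieved with the highest dose of 80 mg Q4W in the study was below the magnitude needed" for maximal lipid lowering. It describes those participants as having hypertriglyceridemia, fatty liver disease and diabetes. The present trial enrols statin-treated people with raised non-HDL-C and TG. Protocol 2.2.4.1 also names 20 mg weekly, which is again 80 mg per 4 weeks.

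**The concern.** ED50 is a dose, so a negative value has no meaning. In the coded function it places a pole at dose = -ED50, and beyond the pole the effect shrinks as dose rises. Any posterior mass there averages impossible curves into the reported means and intervals. The authors bounded the other parameter that must be positive, so the omission looks unintended.

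The second issue is prior influence. A study that stops at 80 mg per month, short of maximal effect, says little about Emax and ED50 separately. If its estimates were nevertheless entered with small variances, the curve at 240 and 320 mg could be pulled towards a wrong value with intervals that are too narrow. SAP Section 5.1 gives dose selection as part of the study objective, and under Protocol 4.1 the 320 mg arm may stop at 10 participants, where a prior would weigh most.

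**Working it through.** **The plan's own figure.** Protocol 9.2 gives SD 17.5, 15% discontinuation and 20 per arm. Completers are 20 × 0.85 = 17. The half-width is 1.96 × 17.5 × √(2/17) = 11.76. Power for a difference of 20 is Φ(20/6.00 − 1.96) = Φ(1.37) = 91.5%. Both match the plan. No design figure is given for the Emax model.

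**Shape when ED50 is negative.** Take E0 = 0 and Emax = −40 (assumed).

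- ED50 = −50: at 80 mg, −40 × 80/30 = −106.7; at 320 mg, −40 × 320/270 = −47.4. The effect shrinks with dose.
- ED50 = −100: at 80 mg, −40 × 80/(−20) = +160; at 120 mg, −40 × 120/20 = −240. The pole lies between two studied doses.

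**Prior mass below zero.** For a normal prior this is Φ(−1/CV), where CV = SD/mean.

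| CV of ED50 prior | Mass below 0 |
|---|---|
| 0.25 | 0.003% |
| 0.5 | 2.3% |
| 1.0 | 15.9% |
| 2.0 | 30.9% |

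An Emax fit to 0, 40 and 80 mg, with 10 to 100 participants per regimen (assumed, because the Phase 2a size is not given), yields an ED50 CV of 0.6 to 4.0, so 5% to 40% below zero. For example, with Emax −60 and ED50 120, the ED50 SD is 341 at n = 10 (CV 2.84, mass 36%) and 108 at n = 100 (CV 0.90, mass 13%).

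**Posterior mass below zero.** These are simulated trials with completers 34/17/34/68/34/34 at 0/80/120/160/240/320 mg (SAP Table 3 × 0.85), SD fixed at 17.5, and independent normal priors as coded.

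| Assumed setting | Mean posterior mass below 0 |
|---|---|
| True ED50 20; prior 100 ± 100 or 60 ± 60 | about 10 to 13% (6 to 12% in repeat runs) |
| Near-plateau by 80 mg; wide prior | 34 to 37% |
| Flat −20 at every dose; Phase 2a-width priors | 13 to 31% |
| Response rising with dose; Phase 2a-width priors | 0.0 to 1.5% |

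In the first two settings, bounding ED50 at zero cuts the posterior SD at 80 mg by about 14 to 30% and moves the 240 and 320 mg means by 1 point or less. With Phase 2a-width priors the shift is at most about 1.4 points at 80 mg and 0.6 points at 240 to 320 mg.

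**Tight, wrongly centred prior.** Assume prior Emax −30 ± 5 and ED50 60 ± 15, with truth −60 and 120. At 320 mg the prior centre implies −30 × 320/380 = −25.3, and the truth is −60 × 320/440 = −43.6. The posterior mean is 4.8 points too small with SD 1.45, an error of 4.8/1.45 = 3.3 SDs, and the 95% interval covers the truth in about 2% of trials. If the arm stops at 10 (8.5 completers), the error is 5.8 points. The placebo mean is pulled too, so the placebo-adjusted errors are 8.6 and 9.4 points. A weak, bounded prior gives 0.7 points placebo-adjusted and 94% coverage.

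**Prior of the width Phase 2a supports.** Mean effects at 240 and 320 mg stay within about 2.3 points of truth, or 3 points with 10 randomized at 320 mg. The worst cases are under the flat −20 truth. A wider prior in the conflict setting above leaves about 1.2 points.

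**The case against.** The best case for the plan has five parts.

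1. The appendix is example code. Starting values and hyperparameters are all placeholders, so it cannot run as printed, and a bound could be added when they are filled in.
2. The two harms need opposite priors. One wide enough to reach below zero is too weak to steer the top doses.
3. The conflict example is severe. Its ED50 CV is 15/60 = 0.25, well under the 0.6 to 4.0 that a 0/40/80 mg study supports. The truth sits 30/5 = 6 prior SDs away on Emax and 60/15 = 4 on ED50. Its centre of −25.3 also disagrees with Protocol 4.3, which expects over 90% probability of at least a 35% reduction at 160 mg Q2W.
4. An early plateau is not what the sponsor expects. Protocol 4.3 treats 80 mg Q4W as minimally efficacious and includes it as a bridging arm.
5. Protocol 9.4.1 presents the Emax curve as illustrative. The per-arm MMRM estimates use no Phase 2a prior and are reported as well, so a large distortion at a top dose would be visible.

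All five stand, and they limit the severity. They do not remove the gap: no other text in the SAP constrains ED50 or plans a prior check, and with the hyperparameters open a reader cannot tell which prior width applies.

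A reader might infer more than this, and the documents do not support it. They do not show that a prior drives the 240 and 320 mg results, since the trial plans 40 participants at each dose. They do not say that Phase 2a enters at full weight, because no variances are stated. Nothing marks the xx entries as redactions. Nor is dose choice tied to the Emax curve: SAP Section 5.1 sets no formal decision rule.

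**Conclusion.** The gap holds as one of specification. ED50 has no positivity bound in the only code given, the hyperparameters are not stated, and the sole prior source is a lower-dose study in a different population with no sensitivity fit.

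The practical size is modest. Under a wide prior and a response close to its plateau by 80 mg, roughly 10 to 37% of posterior mass lies on impossible curves, with the main effect on the 80 mg interval. If the response rises with dose, the problem nearly vanishes. Under a tight and wrong prior, the error at 320 mg is about 5 to 6 points, or 1 to 3 points with priors of the width Phase 2a supports.

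These figures assume the hyperparameters, the Phase 2a sample size, the true curves and a fixed SD of 17.5. Only the SD, arm sizes and discontinuation rate come from the documents. Severity: CONSIDER, because the Emax model supplements the MMRM and leaves the primary analysis untouched.

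**What to change.** Before unblinding, write the prior hyperparameters into the SAP. Add `lower=0` to the ED50 prior, or use a lognormal prior. Refit each Emax model (non-HDL-C, TG, ANGPTL3) once with weakly informative priors, keeping the bound, and show both curves beside the per-arm MMRM estimates.

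The cost is one keyword and one extra run per endpoint. The weak-prior intervals will be somewhat wider. If the response really is flat from 80 mg, the bound truncates one side of the posterior, so its shift at 80 mg (up to about 1.4 points above) need not be towards the truth; the MMRM estimate for that arm is the check. The bound does nothing about a tight, misplaced prior, which is why the refit is needed as well.

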### 9.2. Sample Size Determination

Assuming a common standard deviation of 17.5% (observed in the Month 6 data of the Phase 2a proof-of-concept and dose-ranging study) for the percent change from baseline in non-HDL-C at Week 24 and a treatment discontinuation rate of 15%, 20 participants per arm will correspond to a 95% CI of point estimate  $\pm 11.76\%$  for the difference of treatment effect (versus placebo). These parameters correspond to a power of 91.5% using a 2-sided alpha of 0.05, to detect a difference of -20%, without adjustment for multiple comparison to placebo.

A permutation block schedule will be used in enrollment within each arm, including vupanorsen and matching placebo. If enrollment is stopped for the 160 mg Q2W arm (see [Section 4.1](#)), the corresponding matching placebo enrollment will also be stopped.

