#### 5.2. General Methods

##### 5.2.1. Analyses for Continuous Endpoints

Continuous endpoints will be summarized using the following descriptive statistics: number of subjects, arithmetic mean, standard deviation, median, minimum, maximum. Other descriptive statistics such as standard error, 1st quartile, 3rd quartile, IQR, etc. will

be added where appropriate. They will be summarized and tabulated by treatment groups and visits (including the 12-week safety follow-up visits when available), for the observed data and (percent) change from baseline.

For graphical summaries, mean +/- standard error, LS-Mean +/- standard error will be plotted for the observed data, (percent) change from baseline over time by treatment groups.

For statistical efficacy analyses, an MMRM model featuring the hypothetical estimand will be applied to primary and secondary endpoints, as primary analyses. All eligible post-baseline visits up to and including the analysis visit will be included in the MMRM model, in which baseline value, treatment (categorical), visit (categorical) and interaction term of treatment (categorical) by visit (categorical) will be treated as fixed effects and an unstructured covariance matrix will be used to account for the correlation among visits. If a model convergence issue is encountered with unstructured covariance matrix, then a simpler covariance structure, such as Toeplitz or compound symmetry will be considered. The restricted maximum likelihood (REML) method along with Kenward-Roger adjustment for degrees of freedom will be used for parameter estimation.

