**Table 3. Dose Groups for Dose-response Model**

Total Monthly Dose	Treatment Arm	Injection Regimen	Number of Participants
0 mg	Placebo	Single or double injection Q2W or Q4W	40
80 mg	80 mg Q4W	Single injection Q4W	20
120 mg	60 mg Q2W, 120 mg Q4W	Single injection Q2W, Double injection Q4W	40
160 mg	80 mg Q2W, 160 mg Q4W	Single injection Q2W, Double injection Q4W	80
240 mg	120 mg Q2W	Double injection Q2W	40
320 mg	160 mg Q2W	Double injection Q2W	40

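### The Bayesian Emax model has no baseline term and draws on Week 24 values only, so it gives up available precision and lacks the primary analysis's handling of response-related dropout

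*SAP*

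**What the plan says.** **Emax model.** SAP Section 5.2.1 states that "a Bayesian dose-response model will be constructed to model the relationship between percent change from baseline at Week 24 and doses listed" in Table 3, with Phase 2a estimates as priors for E0, Emax, ED50 and the residual standard deviation. The example code in Appendix 4 agrees with that description: the mean is "mu=e0+emax*dose/(dose+ed50" and its closing bracket, with no further term. SAP Appendix 1 lists the dose-response analysis for non-HDL-C, TG and ANGPTL3 on FAS_primary, with data after intercurrent events excluded, no explicit imputation, and the estimand shown as NA. Section 5.3, on missing data, gives no rule for this model.

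**MMRM.** The primary model in the same Section 5.2.1 has as fixed effects "baseline value, treatment (categorical), visit (categorical) and interaction term" of treatment by visit. It includes every eligible post-baseline visit up to Week 24, and Section 5.3 says that it relies on missing at random.

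**Other Week 24 efficacy models.** The principal stratum regressions (Section 5.2.1.1), the return-to-baseline and retrieved-dropout ANCOVAs (Section 5.3) and the subgroup ANCOVA (Section 6.4) all use baseline. The Emax model is the exception, and no reason is given.

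**The concern.** SAP Section 5.1 gives the study objective as effect estimation and dose selection, and the Emax model is the only dose-response model that the SAP commits to. Two things are lost as it stands.

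- **Precision.** Baseline is already collected and predicts part of the variation in percent change. Without it, that variation stays in the residual, and chance baseline differences between arms of 20 to 40 pass into the curve.
- **Missing data.** The likelihood contains no baseline, no earlier visits and no imputation, so a missing Week 24 value carries no information about the curve, however the software treats it. In effect this is a complete-case fit. Missingness may well be related to earlier response: one intercurrent event, treatment after confirmed severe hypertriglyceridemia (Protocol Sections 8.2.7 and 9.1.1), is itself triggered by an observed lipid value. Protocol Section 2.3.1 also reports ALT rises in Phase 2a that appeared dose dependent, so discontinuation could differ by dose. The documents give no frequencies for either.

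**Working it through.** **Inputs from the documents**
- SD: "Assuming a common standard deviation of 17.5" percent (Protocol 9.2).
- Discontinuation: "a treatment discontinuation rate of 15" percent (Protocol 9.2).
- Size: "20 participants per arm will correspond to a 95% CI of point estimate" ± 11.76% (Protocol 9.2).
- Power: "These parameters correspond to a power of 91.5% using a 2-sided alpha of 0.05, to detect a difference of -20" percent (Protocol 9.2).
- Allocation (SAP Table 3): 40/20/40/80/40/40 at 0/80/120/160/240/320 mg per month, with Q2W and Q4W arms pooled, for example "60 mg Q2W, 120 mg Q4W" at 120 mg.

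**Assumed, because the documents do not give them:** the correlation ρ between baseline and percent change; ED50 of 50 to 400 mg per month; an effect of −40 points at 320 mg; the dropout patterns in step 4.

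**1. The plan's own figure.** 20 × 0.85 = 17 per arm. SE = 17.5 × √(2/17) = 6.00. Half-width = 1.96 × 6.00 = 11.76. Power = Φ(20/6.00 − 1.96) = Φ(1.37) = 0.915. Both stated figures reproduce.

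**2. Emax with and without baseline.** Residual SD after adjustment = 17.5 × √(1 − ρ²), so interval width is multiplied by √(1 − ρ²).

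| ρ | Residual SD | Width ratio | Narrower by |
|---|---|---|---|
| 0.2 | 17.15 | 0.980 | 2.0% |
| 0.3 | 16.69 | 0.954 | 4.6% |
| 0.4 | 16.04 | 0.917 | 8.3% |
| 0.5 | 15.16 | 0.866 | 13.4% |

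In simulations with dropout completely at random, the SE of the placebo-adjusted effect at 160 mg went from 3.30 to 3.17 at ρ = 0.3 (ratio 0.96) and from 3.50 to 3.14 at ρ = 0.5 (ratio 0.90), in reasonable agreement with the formula.

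**3. Emax against the pairwise MMRM contrasts.** Delta-method SE of the placebo-adjusted Emax effect, without baseline or priors, with 85% observed and over the ED50 range:

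| Monthly dose | Emax SE |
|---|---|
| 80 mg | 2.92–3.98 |
| 120 mg | 3.33–3.49 |
| 160 mg | 3.30–3.45 |
| 240 mg | 3.42–3.47 |
| 320 mg | 3.73–3.84 |

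MMRM contrast SE = 17.5 × √(1 − ρ²) × √(1/40 + 1/n). The lower value assumes that all information from missing Week 24 values is recovered; the upper divides by √0.85, so that none is.
- ρ = 0.3: 4.57–4.96 for n = 20; 3.73–4.05 for n = 40.
- ρ = 0.5: 4.15–4.50 for n = 20; 3.39–3.68 for n = 40.

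The unadjusted curve is generally the more precise of the two. At 320 mg they are about equal for ρ = 0.3, and the curve is slightly worse for ρ = 0.5, where they are also about equal at 160 to 240 mg.

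**4. Dropout that depends on earlier response.** Simulated with ρ = 0.3, ED50 = 100 mg, 500 runs per pattern, and a two-visit likelihood equivalent of the MMRM. The chance of a missing Week 24 value rises with a poorer value at the earlier visit.

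| Pattern | Missing overall / placebo | Emax bias | Emax + baseline bias | Largest MMRM bias |
|---|---|---|---|---|
| Moderate | 13% / 24% | 0.5–1.2 | 0.4–1.0 | 0.24 |
| Strong | 12% / 32% | 1.9–2.8 | 1.7–2.4 | 0.15 |

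Bias is in percentage points across the five doses, towards too small an effect. Against the simulated Emax SEs it is 0.52/3.63 = 0.14 to 1.14/3.54 = 0.32 of an SE in the moderate pattern, and 1.91/3.70 = 0.52 to 2.75/3.58 = 0.77 in the strong one. The MMRM figures are of the order of simulation error (about 4 to 5 divided by √500, or 0.2).

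**The case against.** The strongest reply is that this is an additional, illustrative model in an exploratory trial. Protocol Section 9.4.1 presents it as showing the expected relationship, and SAP Section 5.1 plans no formal decision rules. The code is labelled an example, with placeholder priors and no definition of the response variable, so the complete-case reading is an inference. The curve would also differ from the MMRM after any repair, because it pools regimens by monthly dose, imposes a shape and uses Phase 2a priors. With randomisation and no missing data, leaving out baseline costs precision but causes no bias.

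All of this is fair and limits the point. It does not remove it: the prose of Section 5.2.1 names the same three mean parameters and the same Week 24 response as the code, Appendix 1 rules out explicit imputation, and nothing elsewhere supplies baseline, earlier visits or a missing-data rule.

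A reader might infer more than the documents support:
- *That the curve is less precise than the MMRM.* Step 3 shows generally the reverse if the Emax shape is right. The loss is relative to the same Emax model with baseline.
- *That the dose will be chosen from this curve.* No section says so, and optional PK/PD analyses are also foreseen (Protocol 9.4.6, SAP 6.3.2).
- *That it targets the primary estimand.* It shares the analysis set and the exclusion rule, but Appendix 1 lists its estimand as NA.
- *That 15% of participants contribute nothing.* That figure is a planning rate for stopping treatment. Data count as off-treatment only from one dosing interval after stopping, so late discontinuers can still contribute at Week 24.

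**Conclusion.** The point stands in a limited form. As written, the Emax model is in effect an unadjusted complete-case analysis of Week 24 percent change, unlike the baseline-adjusted MMRM and the other modelled Week 24 efficacy analyses. Adding baseline would narrow its intervals by about 2% to 13%, which rests wholly on an assumed correlation of 0.2 to 0.5. The missing-data gap matters more: the bias was about 0.5 to 2.8 points in the assumed patterns, and its size and direction depend on those patterns, including placebo missingness of 24% to 32%. With little dropout, or dropout unrelated to response, that bias would be negligible and only the precision loss would remain. The simulations used no priors; informative priors would change these figures to an extent that cannot be worked out, since the prior values are not given.

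**What to change.** Amend SAP Section 5.2.1, Appendix 1 and Appendix 4 before unblinding, in one of two ways.

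1. **Preferred.** Fit the Emax curve, with its Phase 2a priors, to the Week 24 LS means from the primary MMRM, using their estimated covariance matrix in the likelihood. This carries over both the baseline adjustment and the missing-at-random handling, and uses output that is already planned.
2. **Alternative.** Add beta*(base - mean(base)) to the mean and model the repeated visits jointly. The residual-SD prior must then be re-derived on the baseline-adjusted scale.

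The baseline term without the repeated visits is a one-line change but only a partial repair: in step 4 it left 0.4–1.0 of 0.5–1.2 points of bias, and 1.7–2.4 of 1.9–2.8. Whichever route is taken, the SAP should state how participants without a usable Week 24 value enter the dose-response model. No new data are needed; the cost is SAP wording, modest extra programming and, for the second option, the revised prior.
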